8.4.2. Method of Detecting AEs and SAEs

The method of recording, evaluating, and assessing causality of AE and SAE and the procedures for completing and transmitting SAE reports are provided in Appendix 10.2.

Care will be taken not to introduce bias when detecting AEs and/or SAEs. Open-ended and non-leading verbal questioning of the subject is the preferred method to inquire about AE occurrences.

8.4.3. Follow-up of AEs and SAEs

After the initial AE/SAE report, the Investigator is required to proactively follow each subject at subsequent visits/contacts. All SAEs and AESIs (as defined in Section 8.4.7) will be followed until resolution, stabilization, the event is otherwise explained, or the subject is lost to follow-up (as defined in Section 7.3). Further information on follow-up procedures is provided in Appendix 10.2.

8.4.4. Regulatory Reporting Requirements for SAEs

Prompt notification by the Investigator to the sponsor of an SAE is essential so that legal obligations and ethical responsibilities toward the safety of subjects and the safety of a study drug under clinical investigation are met.

The Investigator is required to submit via email or facsimile the SAE form to the CRO, including a summary of relevant information, a diagnosis or symptom summary, and the Investigator's assessment of its relationship to study drug, within 24 hours. Follow-up information should be provided as it becomes available.

The sponsor has a legal responsibility to notify both the local regulatory authority and other regulatory agencies about the safety of a study drug under clinical investigation. The sponsor will comply with country-specific regulatory requirements relating to safety reporting to the regulatory authority, Institutional Review Boards (IRB)/Independent Ethics Committees (IEC), and Investigators.

Investigator safety reports must be prepared for suspected unexpected serious adverse reactions (SUSAR) according to local regulatory requirements and sponsor policy and forwarded to Investigators as necessary.

An Investigator who receives an Investigator Safety Report describing an SAE or other specific safety information (e.g., summary or listing of SAEs) from the sponsor will review and then file it along with the study binder and will notify the IRB/IEC, if appropriate according to local requirements.

8.4.5. Pregnancy

All pregnancies in female subjects and female partners of male subjects that occur after randomization and the start of study drug administration will be collected through the final visit and up to 3 months after the last dose of the study drug, whichever is later.

If a pregnancy is reported, the investigator should inform the sponsor within 24 hours of learning of the pregnancy and should follow the procedures outlined in Appendix 10.3.

The pregnancy should be followed until delivery or termination of the pregnancy. Abnormal pregnancy outcomes (e.g., spontaneous abortion, fetal death, stillbirth, congenital anomalies, ectopic pregnancy) are considered SAEs.

8.4.6. Hospitalizations for Social Reasons or for Procedures

Hospitalization for social reasons or for procedures that do not generally require hospitalization such as for endoscopy, will not be considered as AEs.

8.4.7. Adverse Events of Special Interest

The treatment-emergent AESIs to be collected are severe opportunistic infections and hypersensitivity reactions of at least moderate severity.

8.5. Treatment of Overdose

Overdose (a dose above the highest dose specified in this protocol) is not expected in this study since the drug is administered by study personnel. No doses of PRV-015 above 600 mg or 8 mg/kg have been previously administered. The effects above these doses are unknown, and no antidote is available.

8.6. Pharmacokinetics and Immunogenicity

Blood samples will be collected at Visit 3 before the first post-randomization dose of study drug administration (baseline) and before the dose is given at each subsequent visit indicated in the SoA. Samples will be analyzed for serum trough concentration of PRV-015 (C_{min}) and ADA, as well as neutralizing antibodies (NAb), using validated assays.

Drug concentration information will not be reported to investigative sites or blinded personnel until the study is unblinded.

8.7. Pharmacodynamics and Biomarkers

Pharmacodynamic biomarkers to be explored in the study include, but are not limited to, the following parameters:

- Biomarkers of disease activity (such as serum IL-15)
- Anti-tTG IgA
- Anti-DGP IgA
- Other exploratory biomarkers

8.8. Genetics

Celiac genetic markers (typically HLA DQ2 and DQ8) will be assessed at screening for inclusion (Section 5.1), if the subject has not already been tested and the results available in the medical record. If a subject has previously obtained a test for HLA, the result will be recorded in the eCRF.

8.9. Quality of Life Measurements

The study personnel will evaluate subjects' quality of life using the ICDSQ questionnaire at study visits specified in the SoA (Section 1.3). The ICDSQ questionnaire (<https://eprovide.mapi-trust.org/instruments/impact-of-celiac-disease-symptoms-questionnaire-c>) is an instrument developed by Alvine Therapeutics to assess the impact of celiac disease symptoms on patients' quality of life (Acaster 2011).

In addition, EQ-5D-5L will be administered to subjects at the same visits as ICDSQ. The EQ-5D-5L is a 6-item, self-administered generic measure of health status and consists of two parts: a descriptive system and a visual analog scale (VAS). (https://euroqol.org/wp-content/uploads/2019/09/EQ-5D-5L-English-User-Guide_version-3.0-Sept-2019-secured.pdf)

ICDSQ and EQ-5D-5L are included in Appendix 10.4.

9. Statistical Considerations

9.1. Statistical Hypotheses

The hypothesis of this study is that one or more dose groups of PRV-015 is effective in attenuating the symptoms of celiac disease compared with placebo in adult subjects with celiac disease who are symptomatic despite being on a GFD for at least 12 months.

9.2. Sample Size Determination

A proposed sample size of approximately 50 evaluable subjects within each treatment group would provide approximately 80% power to detect a 0.40 difference from placebo to any given active treatment group at the two-sided, 0.05 level of significance in the primary endpoint, change through Week 24 in the Abdominal Symptoms domain score in CeD PRO. These calculations are based on the assumption of a █ within-subject standard deviation (SD), as derived in the CELIM-NRCD-001 trial using the mixed effect modeling for repeated measures (MMRM) analyses. An approximate █ difference in the overall least squares (LS) means through 16 weeks in the treatment period was observed between the active (300 mg) and placebo groups. The overall estimate through 16 weeks was observed to be █ for placebo versus █ for the 300 mg treatment group. Of note, the estimated difference at week 16 was █; however, the more conservative overall difference of █ was used in the calculation of sample size. The results and their ranking are exploratory in nature, and the selection of endpoints and dose for confirmatory studies will be based on the totality of evidence. As such, these calculations are not adjusted for multiplicity.

Approximately 220 subjects will be randomized at a ratio of 1:1:1:1 to PRV-015 100 mg, 300 mg, 600 mg, or placebo (approximately 55 subjects per group). Subjects will be stratified by normal or abnormal VH:CD (i.e., <2 or ≥2) and by the CeD PRO Abdominal Symptoms domain score of <3 or ≥3 at baseline using the average of the Abdominal Symptoms domain scores over the last week of the single-blind placebo run-in period immediately before randomization. The number of subjects with Marsh score of 0 or 1 will be capped at approximately 72. Withdrawn subjects will not be replaced.

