Subjects will be assessed for efficacy and safety throughout the study, as indicated in the Schedule of Activities (SoA) (Section 1.3). Clinical assessments occur from Visit 3 through Visit 16. Safety is also assessed at each on-site visit through the end-of-study visit (Visit 16), which takes place 6 weeks after the last planned dose of the study drug.

Randomized subjects will undergo a second EGD and biopsy at the end of the 24-week treatment period, within 7 days of Visit 15 in order to assess changes from baseline in IELs and VH:CD.

Visits 6, 8, 10, and 12 may be conducted either at the site or remotely by certified mobile personnel per the Investigator's decision.

All subjects enrolled in the study will complete the daily eDiary for CeD PRO (at the end of the subject's daily activities, when no more food will be consumed) and for the stool frequency question from Visit 1 through the end of the study at Visit 16, which will encompass the single-blind placebo run-in and the double-blind treatment period and a safety follow-up period.

Safety assessments include clinical laboratory tests, vital signs, and AE assessments. Subjects may undergo unscheduled visits if needed (e.g., for safety reasons).

Disclosure Statement: This is a parallel-group treatment study with 4 treatment groups double blinded to subjects, investigators, and sponsor, preceded by a single-blind placebo run-in period.

Number of Subjects:

Approximately 220 subjects will be randomized (approximately 55 subjects per group). Subjects will be stratified by normal or abnormal VH:CD (i.e., ≥ 2 or < 2) and by the CeD PRO Abdominal Symptoms domain score of < 3 or ≥ 3 at baseline, using the average of the Abdominal Symptoms domain scores over the last week of the placebo run-in period immediately preceding randomization. The number of enrolled subjects with Marsh score of 0 or 1 will be capped at approximately 72. Withdrawn subjects will not be replaced.

A sample size of 50 evaluable subjects within each treatment group would provide approximately 80% power to detect a 0.40 difference between placebo and any given active treatment group at the two-sided, 0.05 level of significance during the 24-week double-blind treatment period in the primary endpoint. See Section [9.2](#) for details.

Treatment Groups and Duration:

After the single-blind placebo run-in phase, subjects will be randomized to one of the 4 treatment groups in a ratio of 1:1:1:1 as follows:

- PRV-015 100 mg q2w

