9.4.1. General Considerations

All continuous endpoints and respective changes from baseline (absolute and percent) will be summarized (N, means, medians, SD, coefficients of variation [CV%], minimum and maximum). Rates or proportions will be tabulated by frequency of occurrence (count) and percent. All summaries will be by treatment and collection time.

Baseline values will be derived from observations collected in the placebo run-in period. For the CeD PRO Abdominal domain scores, baseline value will be the average of scores over the last week of the 4-week placebo run-in period immediately before randomization.

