9.4.2. Primary Endpoint and Estimand

The primary endpoint is the change from baseline through Week 24 in the score of the Abdominal Symptoms domain of CeD PRO questionnaire, compared between the 3 PRV-015 dose groups and the placebo group.

The primary estimand is the difference in the overall mean values (averaged across 24 weeks) of each of the 3 PRV-015 treatment groups compared with placebo of the change from baseline in the Abdominal Symptoms domain of the CeD PRO questionnaire in the target population, regardless of compliance with study treatment or the occurrence of intercurrent events.

The primary endpoint will be tested for each of the 3 dose levels of PRV-015, 100 mg, 300 mg, or 600 mg against placebo, separately as follows:

$$H_{10}: \mu_{PRV015\ (600mg)} = \mu_{Placebo}$$

against the alternative

$H_{11}: \mu_{PRV015 \text{ (600mg)}} \neq \mu_{\text{Placebo}},$

$H_{20}: \mu_{PRV015 \text{ (300mg)}} = \mu_{\text{Placebo}}$

against the alternative

$H_{21}: \mu_{PRV015 \text{ (300mg)}} \neq \mu_{\text{Placebo}}, \text{ and}$

$H_{30}: \mu_{PRV015 \text{ (100mg)}} = \mu_{\text{Placebo}}$

against the alternative

$H_{31}: \mu_{PRV015 \text{ (100mg)}} \neq \mu_{\text{Placebo}}$

The primary efficacy endpoint will be summarized along with respective absolute and percent changes from baseline.

The primary efficacy endpoint (CeD PRO Abdominal Symptoms domain score) will be analyzed using linear mixed effect modeling for repeated measures (MMRM) with treatment, week, and week by treatment as fixed effects, the continuous baseline Abdominal Symptoms domain and VH:CD as covariates, and subject as a random effect.

Baseline Abdominal Symptoms domain score is defined as the average of the daily scores for the last week of assessment in the placebo run-in period. Baseline VH:CD is the measure from endoscopic biopsies performed during the placebo run-in period.

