7 ESTIMATION OF SAMPLE SIZE

A proposed sample size of approximately 50 evaluable subjects within each treatment group would provide approximately 80% power to detect a 0.40 difference from placebo and any given active treatment group at the two-sided, 0.05 level of significance in the primary endpoint, change through Week 24 in the Abdominal Symptoms domain score in CeD PRO. These calculations are based on the assumption of a within-subject standard deviation (SD), as derived in the CELIM-NRCD-001 trial using the mixed effect modelling for repeated measures (MMRM) analyses. An approximate difference in the overall least squares (LS) means through 16 weeks in the treatment period was observed between the active (300 mg) and placebo groups. The overall estimate through 16 weeks was observed to be for placebo versus for the 300 mg treatment group. Of note, the estimated difference at week 16 was however, the more conservative overall difference of was used in the calculation of sample size. The results and their ranking are exploratory in nature, and the selection of endpoints and dose for confirmatory studies will be based on the totality of evidence. As such, these calculations are not adjusted for multiplicity.

Approximately 220 subjects will be randomized at a ratio of 1:1:1:1 to PRV-015 100 mg, 300 mg, 600 mg, or placebo (approximately 55 subjects per group). Subjects will be stratified by normal or abnormal baseline VH:CD (i.e., <2 or \ge 2) and by the CeD PRO Abdominal Symptoms domain score of <3 or \ge 3 at baseline using the average of the Abdominal Symptoms domain scores over the last week of the single-blind placebo run-in period immediately before

Confidential Page

randomization. The number of subjects with Marsh score 0 or 1 will be capped at approximately 72. Withdrawn subjects will not be replaced.

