8.6.1.2 Primary Model

The primary efficacy variable will be analyzed using linear mixed effect modelling for repeated measures (MMRM) assuming data missing at random (MAR) with treatment, week, and week by treatment as fixed effects, the continuous baseline Abdominal Symptoms domain score and VH:CD ratio as covariates, and subject as a random effect.

Baseline Abdominal Symptoms domain score is defined as the average of the daily scores for the last week of the placebo run-in period. Baseline VH:CD is the measure from endoscopic biopsies performed during the placebo run-in period.

The variance-covariance structure to be used is unstructured (UN). If model convergence is not achieved, a first-order auto-regressive structure [AR(1)] will be considered. Additional variance-covariance structure might be explored in case of non-converge issue.

An overall estimate of treatment effect as well as treatment differences for the active treatment groups (600 mg, 300 mg, 150 mg) compared to placebo will be provided along with the respective 95% confidence intervals (CIs). By-week estimates and 95% CI will be provided as well. All tests of statistical significance will be at two-sided, 0.05 level of significance.

The following model will be fitted:

$$Y_{ijk} = \mu + \alpha_j + \gamma_k + \lambda_{jk} + \beta_1 \cdot baseline \ Abdominal \ Symptoms \ score_{ij} + \beta_2 \cdot baseline \ VH; \ CD \ ratio_{ij} + \eta_i + \varepsilon_{ijk}$$

where

 Y_{ijk} is the change from baseline of Abdominal Symptoms weekly domain score for subject i ($i = 1, ..., n_j$) from treatment group j (j = 1, 2, 3, 4) at week k (k = 2, 4, ..., 24),

 μ is the overall mean change from baseline,

 α_j is the fixed effect due to treatment j,

 γ_k is the fixed effect due to week k,

 λ_{ik} is the fixed interaction effect due to treatment j and week k,

 β_1 is the parameter estimate for the baseline Abdominal Symptoms score,

 β_2 is the parameter estimate for the baseline VH:CD ratio,

 η_i is the random effect due to subject i,

 ε_{ijk} is the random error term for subject i from treatment group j at week k.

The observed baseline and post-baseline values along with the change from baseline values (absolute and percent) will also be summarized by treatment group and week (Weeks 2, 4, ..., 24). Baseline and post baseline values for the weekly scores will also be listed.

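### Does calling the planning SD within-subject undermine the stated 80% power?

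*Protocol*

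**What the plan says.** Protocol 9.2 states: "A proposed sample size of approximately 50 evaluable subjects within each treatment group would provide approximately 80% power to detect a 0.40 difference", at two-sided 0.05. The synopsis repeats the claim ("A sample size of 50 evaluable subjects within each treatment group would provide approximately 80% power to detect a 0.40 difference"). The SD is called a "within-subject standard deviation (SD), as derived in the CELIM-NRCD-001 trial using the mixed effect modeling for repeated measures (MMRM) analyses", and SAP 7 likewise says its calculations are "based on the assumption of a within-subject standard deviation (SD), as derived in the CELIM-NRCD-001 trial". The number itself is redacted in both documents, which is not a fault of the plan. Neither text gives a correlation between visits, a between-subject SD or a power formula.

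The quantity tested is the between-arm difference in change from baseline averaged over 24 weeks (Protocol 9.4.2; SAP 3.1 and 8.6.1.1). It is estimated from Weeks 2, 4, ..., 24, which makes 12 visits per subject. For the Abdominal Symptoms domain, "baseline value will be the average of scores over the last week of the 4-week placebo run-in period immediately before randomization". The model has "the continuous baseline Abdominal Symptoms domain and VH:CD as covariates, and subject as a random effect". The SAP 8.6.1.2 equation contains one term that "is the random effect due to subject i" and another that "is the random error term for subject i from treatment group j at week k". Protocol 9.4.2 and SAP 8.6.1.2 both specify an unstructured covariance. The code in SAP 11.4 fits it as a single unstructured residual matrix per subject, with no separate random intercept.

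Both sample-size sections describe the results as exploratory, base dose selection on the totality of evidence and make no multiplicity adjustment.

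**The concern.** In a parallel-group trial, the precision of a treatment difference depends on how much subjects differ from one another. With a simple subject-plus-residual model for change, the variance of one subject's 24-week average is the between-subject variance plus one twelfth of the within-subject variance. A within-subject SD supplies only the second component. Used alone it omits the first, which would overstate power. Used without dividing by 12 it also ignores the gain from averaging, which would understate power. The two effects pull in opposite directions.

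At stake is how a non-significant dose comparison is read. A reader who takes 80% at face value would treat a null result as fairly strong evidence against a 0.40 effect. That would be misplaced if the real planning power were nearer 50%.

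**Working it through.** **Inputs.** From Protocol 9.2: n = 50 per arm, difference 0.40, two-sided alpha 0.05, power about 80%. From SAP 8.6.1.2: 12 visits. The SD is redacted, so 80% cannot be computed forward. All intraclass correlations (ICCs), correlations between visits and compound-symmetry patterns below are assumptions, and complete data are assumed throughout.

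**SD that reproduces the stated figure.** Two-sample normal approximation:

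SD = 0.40 / [(1.960 + 0.842) x sqrt(2/50)] = 0.40 / (2.802 x 0.2) = 0.714.

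The noncentral t gives 0.707. So 80% is exact if an SD of about 0.71 describes a subject's covariate-adjusted mean change over the 24 weeks. The question is what happens if about 0.71 was some other SD.

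**Reading A: total per-visit SD of adjusted change.** This is the square root of a diagonal element of an unstructured residual matrix, the kind the SAP 11.4 code estimates. It already includes differences between subjects. With a common correlation r between visits:

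SD of the 12-visit mean = 0.714 x sqrt[(1 + 11r)/12].

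| r | SD | Power |
|---|---|---|
| 0.5 | 0.525 | 97% |
| 0.7 | 0.608 | 91% |
| 0.8 | 0.645 | 87% |
| 0.9 | 0.680 | 84% |
| 1.0 | 0.714 | 80% |

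Power cannot fall below 80%, because averaging cannot raise the variance above that of one visit.

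**Reading B: within-subject SD of the scores, with baseline and post-baseline scores sharing one stable subject effect.** Adjusting for baseline leaves a between-subject variance of 0.714^2 x (score ICC), so:

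SD of the mean = 0.714 x sqrt(score ICC + 1/12).

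| Score ICC | SD | Power |
|---|---|---|
| 0.5 | 0.545 | 96% |
| 0.7 | 0.632 | 89% |
| 0.8 | 0.671 | 85% |
| 0.9 | 0.708 | 81% |

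Power crosses 80% at score ICC = 1 - 1/12 = 0.917. The limit at score ICC 1 is 0.714 x sqrt(13/12) = 0.743, or 77%. Here a within-subject SD is close to the right input, because the stable subject effect drops out of change.

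**Reading C: residual SD beside a separate subject effect in adjusted change.**

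SD of the mean = 0.714 x sqrt[ICC/(1 - ICC) + 1/12], where ICC refers to adjusted change, not to raw scores.

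| ICC of adjusted change | SD | Power |
|---|---|---|
| 0.2 | 0.412 | 99.8% |
| 0.4 | 0.618 | 90% |
| 0.5 | 0.743 | 77% |
| 0.6 | 0.898 | 60% |
| 0.7 | 1.110 | 44% |

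Break-even is where ICC/(1 - ICC) = 11/12, that is ICC = 11/23 = 0.478.

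**How B and C connect.** Under B, the ICC of adjusted change equals score ICC/(1 + score ICC), which cannot exceed 0.5. The 60% and 44% rows therefore cannot arise from a stable subject effect alone. They need subjects to differ further in their true change, by an amount the documents neither give nor rule out.

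**The case for a change.** The strongest case for a change is that the label, taken at its word, names the wrong variance component. The model descriptions in Protocol 9.4.2 and SAP 8.6.1.2 list a subject effect apart from the residual, which fits Reading C. Under that reading, power could lie anywhere from 44% to nearly 100% over the ICCs shown. Each dose is tested at 0.05, a null result will be compared with the stated power, and the remedy would cost only one look-up and some wording.

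Part of this stands. The wording is loose, the calculation cannot be reproduced from the visible text, and power below 80% cannot be excluded. The prior trial's model code is not in the documents, so Reading A is plausible but not proven.

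The rest does not carry. The fitted model in SAP 11.4 has no separate subject intercept, and adding one to an unstructured matrix would add nothing identifiable. An SD from a model of that kind can already contain the between-subject variation. The low powers need two unverified steps: that about 0.71 was a pure residual SD put into a plain two-sample formula, and that subjects differ greatly in true change. If a repeated-measures formula was used, the back-solved 0.71 is not the residual SD and these tables do not apply. Printing a table of lower powers in the plan would suggest a shortfall that has not been demonstrated.

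**Conclusion.** No change is needed. The 80% is neither confirmed nor contradicted by the visible text. It is exact if the planning SD was about 0.71 for subject-level adjusted mean change. If 0.71 was the total per-visit SD, power is at least 80%. If it was the within-subject SD of scores with a stable subject effect and baseline adjustment, power is 77% or more, and above 80% up to a score ICC of 0.917. Only substantial extra heterogeneity in true change takes it well below 80%. These figures rest on the back-solved SD, 50 complete subjects per arm and compound symmetry.

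Naming the SD and formula would help a reader, but no decision turns on it. The sample size, model and tests stay the same whichever SD was meant. The study is declared exploratory, and the planned 95% confidence intervals show directly whether a 0.40 difference is compatible with the data, so a null result need not be judged against planned power. The SAP already describes monitoring in the past tense (SAP 8.9), so restating planned power now would not alter the trial. This is a missing detail behind a loosely worded label, not an arithmetic error.
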